Establishing the Effectiveness of Publicly Available Smoking Cessation Resource

Study Protocol and Data Analysis Plan

PI: [name], PhD

ClinicalTrials.gov ID: NCT05055778

Funding: This study was funded by the National Center for Advancing Translational Sciences of the National Institutes of Health under Award Number KL2TR003016. [name] was an iTHRIV Scholar during the completion of this work. The iTHRIV Scholars Program is supported in part by the National Center for Advancing Translational Sciences of the National Institutes of Health under Award Numbers UL1TR003015 and KL2TR003016.

List of Abbreviations

NCI: National Cancer Institute

SFTXT: Smokefree.gov Initiative SmokefreeTXT smoking cessation text message intervention

Study Overview

This project will recruit smokers from across Virginia with recruitment from rural and non-rural counties. All participants will be provided with access to a research version of the National Cancer Institute's SmokefreeTXT program (SFTXT). Cessation outcomes will be assessed at the end of program (7-weeks), and 3- and 6-months from enrollment. We will compare smoking abstinence by rurality. The project will be conducted remotely, using study-specific websites to complete all data collection, and using participants' own phones for intervention implementation.

Study Recruitment

Participants will be recruited using targeted (by location and likelihood of being a smoker) Google advertisements, social media (e.g. Facebook), and via introduction by a representative of a community partner organization. People interested in learning more about the study will be able to click through to a secure study-specific Qualtrics page which will serve as the study website. The website will include all information needed for informed consent and, for eligible participants, will serve as the consent form. It will provide an overview of the study and describe all aspects of study participation, risks, and benefits.

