complete online follow-up assessments. The assessment questionnaires include questions about tobacco use, reasons for relapse (if relevant) motivation to quit smoking (if relevant), confidence in quitting (if relevant), mood, cessation techniques used in the previous assessment period, alcohol use, as well as satisfaction with the intervention and any changes in cell phone and technology use (e.g., type of phone, carrier, frequency of voice calls, frequency of text messaging, perceived quality of signal quality, etc.). The Post-Assessment Questionnaires are estimated to take no more than 20 minutes. As was true for the Pre-Assessment, participants will be able to complete the Post-Questionnaires in more than one sitting as the program auto saves where they are in the Questionnaire. Participants will be able to review and revise answers up until the point they select “Submit.” Once the Questionnaire data is submitted, participants will no longer have access to their responses on the Questionnaire. All participants will receive reminder emails to complete the assessments daily for 3 days after the invitation to participate is sent.

Intervention

SFTXT is a six- to eight-week program that takes place entirely on a user’s cellphone. Adults who interested in quitting smoking register for the program either online or by texting the program directly and select a quit day up to two weeks in the future. Between enrollment and the quit day, three to five messages are sent each day in preparation for the quit attempt. Starting on the quit day, users continue to receive multiple messages a day for six weeks. Within-program assessment questions texted to users measure smoking status, mood, and craving levels. Users are also able to request on-demand help using “keywords” related to smoking, mood, and cravings. Use of a keyword returns one of several preprogrammed responses. In practice, users are told about the keywords initially and are given reminders about some or all of the keywords within the program on Days 1,6, 10, 14, 17, 20, and 35. Users may opt out of the program at any time by texting “STOP” and can restart the program with a new quit date by texting “NEW”. SFTXT is one of the most popular publicly available text-messaging cessation interventions, with more than 150,000 smokers having enrolled since 2011.

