For the purposes of this study, all messages from SFTXT have been reprogrammed into a study specific account on a third party text message vendor, TextIT, and administered through a verified phone number via Twilio. This will allow better control of text message delivery and data by study staff, while maintaining all program functionality. For study participants, the initial quit date is set at one week after enrollment, but participants may change their quit date at any time by texting “NEW”.

Study End

After completion of the 6-month survey, participants will be told that they have reached the end of the study. Participants who do not respond to the invitation to complete the 6-month post-assessment after four reminder emails will be sent an email informing them that they have reached the end of the study

Participant incentives

Participants will receive up to \$100 for participating in the study in the form of e-gift cards sent at three time points:

- Up to \$30 at the end of the intervention
 - \$10 for completing the pre-cessation survey
 - \$20 for completing the end of intervention survey
- \$30 for completing the 3-month survey
- \$40 for completing the 6-month survey

Data Analysis

This study was approved by the Social and Behavioral Sciences IRB at the University of Virginia (SBS IRB# 3928, clinicaltrials.gov identifier: NCT05055778).

Analysis of this study will be primarily descriptive in nature as there is only one intervention arm and no randomization

Outcomes of Interest

The post-intervention, three-, and six-month assessments measure the primary outcome of interest: 7-day smoking abstinence (responses to the question: “Have you smoked a cigarette (even a puff) in the past 7 days?”, with responses of ‘yes’, and ‘no’) measured at 7-weeks, 3-months, and 6-months. Secondary outcomes include continuous smoking abstinence (responses to the question: “In the last [6-weeks/3 months/6 months], have you smoked at all?”, with responses of ‘yes’, ‘no’, and ‘don’t know’). To provide the most conservative estimates of abstinence, missing responses for each assessment will be coded as continuing to smoke.

Statistical Analyses

Descriptive statistics will be used to characterize the population and describe primary and secondary cessation outcomes in the entire study population. All analyses will be conducted using SAS 9.4 (SAS Institute Inc., Cary, NC).

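### Coding missing as smoking is conservative for one abstinence rate, but as the only missing-data rule it can bias the rural versus non-rural comparison in either direction

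*Combined protocol and SAP*

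**What the plan says.** The Study Overview announces one between-group comparison: "We will compare smoking abstinence by rurality". The primary outcome is self-reported 7-day abstinence at 7 weeks, 3 months and 6 months, and continuous abstinence is secondary. For both, Outcomes of Interest states: "To provide the most conservative estimates of abstinence, missing responses for each assessment will be coded as continuing to smoke".

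No other treatment of missing data appears: no respondent-only analysis, imputation, weighting or bounds, and no commitment to report response by rurality. The Statistical Analyses section says only that descriptive statistics will "describe primary and secondary cessation outcomes in the entire study population"; it does not say how the rurality comparison will be done.

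Follow-up is by online survey, invited by email. On reminders, Post-baseline Assessments says: "All participants will receive reminder emails to complete the assessments daily for 3 days after the invitation to participate is sent". The Intervention section describes a second source of smoking data: "Within-program assessment questions texted to users measure smoking status, mood, and craving levels".

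**The concern.** Under this rule each group's reported rate is its response rate multiplied by abstinence among its responders. A comparison of two such rates mixes two things: who quit, and who answered an emailed survey. If the groups differ in response, or in how often non-responders are in fact abstinent, the coded difference can create, hide, shrink or exaggerate a rural difference.

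The comparison by rurality is the only between-group comparison the study announces. With the coded rates alone, and no commitment to show response by group, a reader of the results could not separate the two explanations.

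**Working it through.** The plan states no sample size, expected abstinence or expected response, so there is no figure of its own to reproduce. The rule and the comparison come from the document; every rate below is an assumption chosen to show the mechanism.

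**Notation.** For each group, r is the response rate, p is abstinence among responders and q is abstinence among non-responders. Subscripts are R for rural and N for non-rural. The target is the self-reported rate that full response would have given.

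**One rate.**
- Full-response rate: T = r·p + (1 − r)·q
- Coded rate: C = r·p
- Bias: C − T = −(1 − r)·q, which is never positive. The rule is a lower bound, as the plan says.

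**The difference, rural minus non-rural.**
- Bias = (C_R − C_N) − (T_R − T_N) = (1 − r_N)·q_N − (1 − r_R)·q_R

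This is zero only when the share both missing and abstinent is equal in the two groups, for example when q = 0 in both. Otherwise it has either sign.

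**Example 1: unequal response.** Let p = 25% in both groups, r_N = 80% and r_R = 65%. The coded rates are 0.80 × 0.25 = 20.0% non-rural and 0.65 × 0.25 = 16.25% rural, a difference of −3.75 points. That same coded result arises from quite different truths:

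| q_N | q_R | Full-response N | Full-response R | True difference | Bias |
|---|---|---|---|---|---|
| 25% | 25% | 25.0% | 25.0% | 0 | −3.75 |
| 10% | 10% | 22.0% | 19.75% | −2.25 | −1.50 |
| 0 | 0 | 20.0% | 16.25% | −3.75 | 0 |
| 25% | 10% | 25.0% | 19.75% | −5.25 | +1.50 |

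In the last row a rural deficit is understated. Swapping the two response rates in the first row gives 0.35 × 0.25 − 0.20 × 0.25 = +3.75 points.

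**Example 2: equal response.** Let r = 75% and p = 25% in both groups, q_N = 15% and q_R = 5%. Both coded rates are 18.75%, so the reported difference is 0. The full-response rates are 18.75 + 0.25 × 15 = 22.5% non-rural and 18.75 + 0.25 × 5 = 20.0% rural, a true difference of −2.5 points.

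**Two-sided range.** Let abstinence be 20% in both groups and let non-responders resemble responders. The bias is then 0.20 × (r_R − r_N):
- response 60% rural, 80% non-rural: 12% versus 16%, −4 points; reversed, +4 points
- response 60% rural, 90% non-rural: 12% versus 18%, −6 points; reversed, +6 points

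Keep the overall 20% and the 60%/80% response, but let non-responders be abstinent half as often as responders. Then p = 0.20/(r + 0.5(1 − r)), the coded rates are 15.0% and 17.78%, and the bias is 2.8 points in size. At a quarter as often it is 1.7 points; at never, 0.

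**A real difference.** Let true abstinence be 15% rural and 20% non-rural (−5 points), with non-responders like responders:
- response 80% rural, 60% non-rural: 12% versus 12%, coded difference 0
- response 70% in both: 10.5% versus 14%, −3.5 points
- response 60% rural, 80% non-rural: 9% versus 16%, −7 points

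**The case against.** The strongest reply is that the study is single-arm, non-randomised and mainly descriptive, and that the rurality comparison rests on one sentence in the Study Overview. The Statistical Analyses section does not define it, which is a more basic gap than how its missing data are handled. Moreover, the plan calls the rule conservative only for estimates of abstinence and never for a difference, so it makes no false statement.

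That is fair: this is an omission, not a contradiction. But a described contrast is biased just as a tested one is, and if the announced comparison is made, the only stated rule governs it.

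The size is also hypothetical. Nothing in the document shows that response differs by rurality or in which direction. Payments of $20, $30 and $40 for successive follow-up surveys, and the four reminder emails mentioned under Study End, may keep non-response down. This stands as a caution on size; neither measure removes the mechanism.

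Response by rurality could be counted from data in hand even though the plan does not ask for it. True, but the plan does not commit to showing it. Finally, no remedy identifies the answer. A respondent-based estimate assumes that non-responders resemble responders, texted answers come from the same participants (who may opt out), and with no stated sample size multiple imputation may not be feasible. These limits argue for a modest remedy.

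**Conclusion.** The concern holds. Missing = smoking is a valid lower bound for each self-reported abstinence rate, but it has no conservative direction for the rural versus non-rural difference, and the plan offers nothing beside it. The mechanism is algebra and is certain; its size in this study is unknown. Under assumed response of 60% to 90%, 20% abstinence in both groups and non-responders like responders, the bias runs from −6 to +6 points. It shrinks as non-responders are less often abstinent and vanishes if none are.

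The lower-bound property is relative to self-report under full response. The document describes no biochemical verification, so over-reporting by responders is a separate matter. The whole-sample descriptive result is not undermined; the announced comparison should not rest on the coded rates alone.

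**What to change.** Keep missing = smoking for the whole-sample rates and state that it is conservative for those rates only. For the rurality comparison, add to Statistical Analyses:

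1. A table of response by rurality at 7 weeks, 3 months and 6 months.
2. Beside the coded result, a respondent-based estimate or, if numbers allow, a multiple-imputation estimate using baseline data, earlier survey reports of smoking and the texted smoking-status answers (mainly useful for 7 weeks).
3. A short sensitivity table in which abstinence among non-responders runs from zero to the responder rate and may differ between rural and non-rural participants.

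Interpret the rural difference in light of all three. The cost is one paragraph and modest SAS work on data already being collected, with no further participant contact. The drawback is that the comparison will carry more than one figure.
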